## 9.4.7 Incidence of UOM

The incidence of UOM will be calculated as the percent of patients within each treatment group who have at least one WHO score ≥2. The incidence of patients with UOM will be compared between treatment groups using the chi-square test.

## 9.4.8 Assessment of Pain

At each study visit, the patient's assessment of their pain over the previous 24 hours will be recorded by study personnel using a scale of 1-10. Descriptive statistics of pain assessments will be summarized by visit, including change from baseline. The Wilcoxon rank sum test will be used to compare the pain scale between treatment groups at each visit.

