5.2. Secondary Objectives

To assess the impact of SGX942 compared to placebo on the following clinically important secondary objectives:

- To assess the impact that SGX942 has on the Area-Under-the-Curve (AUC) for SOM (WHO Grade ≥3) by time plot (severity-weighted duration)
- 2. To assess the impact that SGX942 has on the Area-Under-the-Curve (AUC) for ulcerative oral mucositis (UOM; defined as WHO Grade ≥2) by time plot (severity-weighted duration)
- 3. To assess the impact that SGX942 has on the incidence of SOM
- 4. To assess the impact that SGX942 has on the quality of life assessment using the EORTC QLQ-C30 (version 3) and QLQ-H&N43 instrument
- 5. To assess the impact that SGX942 has on the amount of opioids used

To assess the impact of SGX942 compared to placebo on the following additional secondary objectives:

- To assess the impact that SGX942 has on the cumulative number of days of RT breaks
- To assess the impact that SGX942 has on the duration of SOM; in all randomized patients receiving fractionated RT and concomitant cisplatin chemotherapy, given as 80-100 mg/m² (ITT population)
- To assess the impact that SGX942 has on the duration of UOM
- To assess the impact that SGX942 has on the cumulative amount of pain reported by patients
- The duration of SOM using an alternative definition calculated as the number of days from the first oral examination with WHO grade ≥3 through the last assessment with a WHO score ≥3 (and not to the first assessment with a WHO grade <3) with no further reports of a WHO grade ≥3
- The duration of SOM in the Per-Protocol Population defined as patients receiving a cumulative radiation dose of at least 55 Gy and study drug twice per week during and for 2 weeks after radiation therapy

Original: 11 January 2017 Confidential Page 28 of 67

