10.2.2.4. Assessment of Pain

At each study visit, the patient's assessment of their pain over the previous 24 hours will be recorded by study personnel using a scale of 1-10. Patients with missing visits will have their pain estimated for the missing data by averaging their pain scores reported using the formula detailed in the SAP.

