## 3.3 METHODOLOGY AND CONVENTIONS

Safety and efficacy data will be summarized and presented by treatment group (SGX942 and placebo) in summary tables. Continuous variables will be presented by descriptive statistics including n, mean, standard deviation, median, minimum, and maximum. Categorical variables will be tabulated by frequency count and percentage.

Unless otherwise stated, all statistical tests will be two-sided hypothesis tests performed at the 5% level of significance for main effects, and all confidence intervals will be two-sided 95% confidence intervals. All analyses will be performed using SAS® Version 9.3 or higher.

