#### 9.3.2 Other Secondary Endpoints

- Comparison of the cumulative number of days of RT breaks (mITT population)
- Comparison of the duration of SOM; in all randomized patients receiving fractionated RT and concomitant cisplatin chemotherapy, given as 80-100 mg/m² (ITT population)
- Comparison of the duration of UOM (mITT population)
- Comparison of the cumulative amount of pain reported by patients (mITT population)

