#### 4. MISSING DATA FOR SOM DURATION CALCULATIONS

As noted above (Section 9.1), the primary analyses will examine the duration of SOM and censor the patient's data when missing. For clarity, censored visits will carry forward the last WHO score recorded for the subject through to discontinuation. For sensitivity analyses, the data will be analyzed assuming that the SOM remains at the last recorded WHO grade for the entire trial (irrespective of early study termination) and, again, assuming that the SOM was 0 throughout the trial period.

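### Cumulative pain is listed as a secondary endpoint but never derived: the SAP's only stated pain test is repeated at each visit, and the missing-visit formula promised by the protocol is absent

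*SAP*

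**What the plan says.** Protocol 5.2 sets the objective: "To assess the impact that SGX942 has on the cumulative amount of pain reported by patients". SAP 9.3.2 carries it over as an other secondary endpoint: "Comparison of the cumulative amount of pain reported by patients (mITT population"). SAP 2.2.2 lists it in the same way.

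SAP 9.4 announces that the calculation procedures for the endpoints follow. For pain, 9.4.8 has three elements: a 1-10 rating of the previous 24 hours at each study visit; "Descriptive statistics of pain assessments will be summarized by visit, including change from baseline"; and "The Wilcoxon rank sum test will be used to compare the pain scale between treatment groups at each visit".

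For missed visits, protocol 10.2.2.4 says patients will have their "pain estimated for the missing data by averaging their pain scores reported using the formula detailed in the SAP". The SAP's only missing-value rule for an efficacy score is Appendix 1, item 4, headed "MISSING DATA FOR SOM DURATION CALCULATIONS".

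The level of each test comes from SAP 3.3: "Unless otherwise stated, all statistical tests will be two-sided hypothesis tests performed at the 5% level of significance for main effects". The fixed-sequence procedure in SAP 9.3.1 covers five other endpoints and does not include pain.

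**The concern.** The endpoint is one quantity per patient: how much pain was accumulated over the course. The stated method answers a different question, whether pain differs between arms on a given visit, and asks it many times. A programmer working from 9.4.8 has no sum, area, time window or per-patient value to compute.

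Two things are at stake. First, the comparison promised in 9.3.2 would have to be defined after the fact, possibly after unblinding, with a choice between sum and area, between windows and between missing-data rules. Second, the output that is defined is a long row of unadjusted p-values. One significant visit could be presented as a pain benefit even if there is no overall effect.

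One of the tests is also hard to interpret. The post-RT week 5 visit takes place only if the week 4 WHO score is 2 or more. That test therefore compares subsets selected after randomisation on mucositis severity, which is what the drug is meant to change.

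**Working it through.** The documents state no design figure for pain, so there is none to reproduce. The check has three parts.

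**1. Pain set beside its neighbours in SAP 9.4**

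| Endpoint | Per-patient quantity | Window | Between-arm test |
|---|---|---|---|
| RT breaks (9.4.6) | Sum of break days | Through final RT | One ANOVA |
| Opioid use (9.4.9) | Total, oral morphine equivalent | Baseline to 6 weeks post-RT | Total compared by ANOVA |
| Pain (9.4.8) | None | None | Wilcoxon at each visit |

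The missing-visit cross-reference fails. Protocol 10.2.2.4 points to the SAP, and the SAP has no formula for pain. SAP Appendix 1, item 5 describes the protocol's missing-data method as last value carried forward, which is not the averaging rule that the protocol gives for pain.

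**2. Number of tests**

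The inputs are the pain row of the schedule (protocol Table 7, SAP Table 1) and its 7-week RT assumption.

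- Weeks 1-9, two visits a week: 9 x 2 = 18.
- Post-RT weeks 3, 4, 5 and 6: 4.
- Post-baseline to 6 weeks post-RT: 18 + 4 = **22**, or **21** without the conditional week 5 visit.
- Adding the 12-week and 12-month visits: 22 + 2 = **24**. Adding Baseline as well: 25.
- In general, with R weeks of RT: 2(R + 2) + 4, less 1 if week 5 is not held. R = 5 gives 17-18 and R = 6 gives 19-20.

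**3. False positives if the drug has no effect on pain**

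Each test is two-sided at 0.05 (SAP 3.3).

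- Expected number: 22 x 0.05 = **1.1**, whatever the correlation.
- Probability of at least one with independent tests: 1 - 0.95^k. This is 0.582 for k = 17, 0.659 for 21, **0.676** for 22 and 0.708 for 24.

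Repeated pain scores from one patient are correlated, so independence is the upper end. The documents give no correlation, so I assumed values from 0 to 0.95. I simulated 22 correlated null z-statistics (400,000 replicates) under two structures: equal correlation between all visits, and first-order serial correlation, AR(1), that decays with distance.

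| Correlation | Equal | AR(1) |
|---|---|---|
| 0 | 0.676 | 0.676 |
| 0.5 | 0.439 | 0.618 |
| 0.7 | 0.300 | 0.530 |
| 0.8 | 0.233 | 0.453 |
| 0.9 | 0.159 | 0.329 |
| 0.95 | 0.119 | 0.233 |

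The range is roughly **12% to 68%**, and every value exceeds 5%. One test on one score per patient would have a type I error of 0.05. Keeping the 22 tests as inference under Bonferroni would need 0.05 / 22 = 0.0023 each.

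**The case against.** The strongest reply is that this matters little for decisions. Pain is outside the hierarchy, type I error control is claimed only for the five ordered endpoints, and unadjusted by-visit p-values are ordinary supportive output. That stands, and it limits the importance of the point. It does not supply the missing derivation.

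A reader might infer more than the documents support, in four ways.

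- *That a chance positive is likely.* This depends on the unknown correlation. At 0.8 or above both structures give less than even odds. The figures also count differences in either direction. Counting only tests that favour SGX942, the probability is 43% if independent, 24% (AR(1)) or 12% (equal) at 0.8, and 17% or 8% at 0.9. The supportable statement is inflation above 5% by an amount that cannot be fixed from the documents.
- *That no cumulative result will be produced.* SAP 9.3.2 still commits to the comparison. It is undefined rather than withdrawn, and the table shells are a separate document not available here. A derivation placed there would still not be in the SAP, where the protocol says the formula is.
- *That visits are misaligned throughout because RT length varies.* Protocol 6.1 schedules post-RT visits from the last RT session, and study drug visits start within 3 days of RT start. Misalignment arises mainly around the end of RT, or if visits are pooled by study week, which 9.4.8 does not specify.
- *That a time-averaged score is the natural remedy.* Area divided by days covered is average pain. Two patients with the same average but different course lengths have different cumulative pain. A patient who leaves before pain peaks would be scored on low-pain days only.

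**Conclusion.** The point holds as a specification gap in a non-hierarchical secondary endpoint. The endpoint is listed in both documents, no cumulative score is derived in either, and the protocol's reference to an SAP formula leads nowhere. This part rests on the text alone and needs no assumption.

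The multiplicity part is secondary. It amounts to 22 tests to 6 weeks post-RT (21 or 24 on other readings of each visit), 1.1 expected false positives, and a 12% to 68% chance of at least one. It assumes 7 weeks of RT, all visits held, no adjustment, and a correlation between 0 and 0.95. The primary test and the five ordered secondary endpoints are not affected.

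**What to change.** In SAP 9.4.8:

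1. Derive one cumulative pain score per patient from baseline to 6 weeks post-RT, the window that 9.4.9 uses for opioids. Either area under the pain-time curve or a sum would serve, provided one is fixed in advance. Visits change from twice weekly to weekly, so a plain sum gives the treatment period more weight per day, whereas the area allows for the spacing.
2. Fill missed visits with the averaging rule that protocol 10.2.2.4 names, and write out its formula. Because averaging also scores an early leaver on the visits attended, report the number of filled visits by arm. Reconcile the last-value wording in Appendix 1, item 5.
3. Compare arms with one two-sided Wilcoxon rank sum test in the mITT population.
4. If wanted, add area divided by days covered as a sensitivity analysis for unequal RT length.
5. Keep by-visit pain summaries as descriptive output without p-values.

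The cost is SAP wording and one derived variable. No new data are collected, and the sample size does not change.

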## 9.4.9 Amount of Opioid Medication Used

At each study visit, study personnel will record the amount of opioid medication that the patient reports having taken over the previous 24 hours. Type and usage of medication will also be collected. Descriptive statistics of the amount of opioid medication used, normalized to a calculated oral morphine equivalent, will be summarized by visit. Total opioid used will be summarized though the treatment period (baseline through 6 weeks post-radiation treatment) and compared between treatment groups. Values will be compared between treatment groups using a one-way ANOVA test. Mean  $\pm$  standard deviation will be plotted for each visit.

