6.2.4 History of Pain and Opioid Use

Except for the Screening visit, at every study visit, the study staff will review with the patient their current pain level as well as the cause of their pain. Efforts will be made to differentiate pain due to OM versus other causes of pain. The study staff will also review with the patient their current prescriptions for pain medication (opioids) with special care taken to review the as needed medications the patients have been given as well as the frequency with which they are taking them. Details for all of the above will be recorded in the eCRF.

In addition, site staff will review the study-specific oral hygiene requirements with the patient on a weekly basis.

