6.3. Visit Schedule

6.3.1 Screening

The Screening visit must be done within 4 weeks prior to the Baseline visit. Prior to starting the study medication, the results of all tests must be reviewed to assure that the patient meets all entry criteria. Procedures to be done at this visit are:

- Obtain Informed Consent Form (ICF) signature
- Assure that the initial tumor imaging is compatible with RECIST Criteria (CT, MRI, or PET scans)
- Assure that the tumor was evaluated for HPV status
- Assessment of entry criteria
- Complete Medical History
- Complete Physical Examination
- Vital Signs
- Serum HCG pregnancy test (women only)
- Hematology Panel
- Clinical Chemistry Panel

6.3.2 **Baseline Day**

Baseline assessment will be completed prior to radiation, chemotherapy, and study drug administration but within 96 hours of the initial study drug treatment. Patient will be seen on the first day of study drug treatment. The entry criteria will be reviewed and an interim medical history taken to assure that the patient meets all entry criteria. If the patient still qualifies, they will undergo the following procedures:

Confidential

- Interim Medical History
- Randomization
- Vital signs
- Adverse events (begin collecting after randomization)
- Physical Exam
- Hematology Panel (if more than 7 days from Screening sample)

- Clinical Chemistry Panel (if more than 7 days from Screening sample)
- Clinical evaluation of mucositis (WHO Score)
- Quality of Life assessment
- Serum Pregnancy (if more than 7 days from Screening sample)
- History of pain and opioid medication use
- Assessment of Infections

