10.2.1.5. Amount of Opioid Medication Used

At each study visit, study personnel will record the amount of opioid medication that the patient reports having taken over the previous 24 hours. Each type of medication and whether it was used because of OM pain or other types of pain will be noted in the eCRF. Each opioid dose will be converted to an "oral morphine dose equivalent dose" and the total amount of opioid used for each patient summed over each visit from baseline to 6 weeks post-completion of the radiation therapy. Patients with missing visits will have their opioid usage estimate for the missing data by using an average of their opioid use for the available visits using formula detailed in the SAP. The mean and median amount of total opioids used in each of the treatment groups will be compared.

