#### 9.3 ANALYSES OF SECONDARY ENDPOINTS

## 9.3.1 Hierarchical Secondary Endpoints

Multiple endpoints in this trial are expected to be clinically important. To control type 1 error, the following five secondary endpoints will be tested in a fixed sequence, hierarchical test procedure. In this procedure, a sequential comparison of the groups for each endpoint will be calculated with unadjusted p-values. If the test is statistically significant, the null-hypothesis that the groups are the same will be rejected and testing of the next endpoint will be done. Once an analysis has a p-value above the threshold, no further endpoints will be formally tested. All 5 analyses will be conducted in the mITT population. The hierarchical orders of these endpoints are:

- 1. Comparison of the AUC for SOM (WHO Grade >3) by time plot (severity-weighted duration)
- 2. Comparison of the AUC for UOM (defined as WHO Grade ≥2) by time plot (severity-weighted duration)
- 3. Comparison of the incidence of SOM
- 4. Comparison of the quality of life assessment using the EORTC QLQ-C30 and QLQ-H&N43 instrument
- 5. Comparison of the total amount of opioids used

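### Total opioid use, the fifth hierarchical secondary, is tested without the baseline dose the trial already records: the test is valid but loses precision that could be recovered at no cost

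*SAP*

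**What the plan says.** SAP 9.3.1 states that "the following five secondary endpoints will be tested in a fixed sequence, hierarchical test procedure", and the fifth of these is "Comparison of the total amount of opioids used", in the mITT population.

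SAP 9.4.9 converts doses to oral morphine equivalents and says: "Total opioid used will be summarized though the treatment period (baseline through 6 weeks post-radiation treatment) and compared between treatment groups". It names the test: "Values will be compared between treatment groups using a one-way ANOVA test". No covariate is mentioned.

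Protocol 10.2.1.5 defines the quantity as "the total amount of opioid used for each patient summed over each visit from baseline to 6 weeks post-completion of the radiation therapy", each visit contributing the amount taken in the preceding 24 hours. The baseline visit is therefore one of the terms. Protocol 6.3.2 (Baseline Day) places that visit before radiation, chemotherapy and study drug, and lists "History of pain and opioid medication use" among its procedures.

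The reason for use is also collected. Protocol 10.2.1.5 says: "Each type of medication and whether it was used because of OM pain or other types of pain will be noted in the eCRF". Protocol 6.2.4 adds: "Efforts will be made to differentiate pain due to OM versus other causes of pain". Neither document restricts the tested total by reason.

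Opioid use is not among the exclusion criteria (protocol 7.2) or the prohibited therapies (8.2). Randomisation is stratified by site, gastrostomy tube and HPV status (8.4), not by opioid use.

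**The concern.** A patient who enters on a steady opioid dose for tumour, surgical or other pain contributes that dose at every visit, whatever happens to the oral mucosa. The first term of the sum is measured before study drug and cannot respond to it. If such patients are present, their prior use adds variance between patients that has nothing to do with treatment. The plan collects the one variable that would remove much of that variance and then leaves it out of the test.

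What is at stake is the power of a formally tested step in the hierarchy and the width of the confidence interval for the treatment difference. The neighbouring pain analysis (SAP 9.4.8) reports change from baseline; the opioid analysis has no counterpart.

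**Working it through.** **The plan's own figure.** The only sample-size figure is for the primary endpoint: 95 evaluable per arm, 190 in total, from medians of 13 and 8 days at 90% power and two-sided 0.05. With HR = 8/13 = 0.615, Freedman's formula gives (1.960 + 1.282)² × [(1 + HR)/(1 − HR)]² = 10.51 × 4.2² ≈ 186 events, within 3% of 190 (Schoenfeld gives 179). The figure reproduces, but it says nothing about opioids. No mean, SD, prevalence of prior use or correlation is given for this endpoint, so everything below rests on stated assumptions.

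**How much a stable prior dose adds.** On a 7-week RT course the protocol's Table 7 gives 1 baseline visit, 2 × 9 = 18 dosing visits and 4 later visits (weeks 3 to 6 post-RT), 23 in all. The week 5 post-RT visit takes place only if the week 4 WHO score is 2 or more, so a patient without mucositis has 22. For an assumed stable 30 to 40 mg/day taken for other pain:

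- 22 × 30 = 660 mg; 22 × 40 = 880 mg.
- Without the baseline visit: 21 × 30 = 630 mg; 21 × 40 = 840 mg.

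These are sums of recorded 24-hour amounts, not full consumption. Dropping the baseline visit removes one term in 22, so it does little alone; the covariate does the work. In a linear model that includes baseline dose, adding that dose to the outcome or leaving it out changes only its own slope. The treatment estimate and its standard error stay the same.

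**Gain from linear baseline adjustment.** With correlation r between baseline dose and the later total, residual variance is 1 − r² of the unadjusted variance, and the unadjusted test needs 1/(1 − r²) times as many patients for equal precision. Power is Φ(δ√(n/2)/√(1 − r²) − 1.960). With n = 95 per arm and an assumed standardised effect δ = 0.40, δ√(n/2) = 2.757.

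| r (assumed) | 1 − r² | Variance removed | 1/(1 − r²) | Power |
|---|---|---|---|---|
| 0 (as planned) | 1.00 | 0% | 1.00 | Φ(0.797) = 0.787 |
| 0.3 | 0.91 | 9% | 1.10 | 0.824 |
| 0.5 | 0.75 | 25% | 1.33 | 0.889 |
| 0.6 | 0.64 | 36% | 1.56 | Φ(2.757/0.8 − 1.960) = 0.931 |

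**Simulation check with skewed doses.** The check used 95 per arm and 4,000 runs per setting. It assumed that 35% enter on opioids (lognormal, median 30 mg, log-SD 0.7), that the mucositis-related dose is lognormal (median 40 mg, log-SD 0.8), and that treatment cuts that dose by 30%.

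| Share of baseline dose that persists | ANOVA on total | ANCOVA with baseline dose |
|---|---|---|
| Half | 0.70 | 0.74 |
| All | 0.59 | 0.74 |

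With no treatment effect, rejection rates for all methods lay between 0.041 and 0.054.

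**The case against.** The strongest reply is that nothing here is wrong. A reader might infer that prior opioid use biases the comparison or could produce a false positive. The documents do not support that: allocation is randomised 1:1 and double-blind, and chance imbalance in baseline dose is already reflected in the ANOVA standard error. The simulated null results agree. This stands in full.

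A reader might also infer that counting opioids taken for any reason is an error. The stated objective (protocol 5.2, SAP 1.2.1) is the amount of opioids used, without qualification, and attributing each dose to mucositis is a judgement made at the visit. An all-cause total avoids depending on that judgement. This stands too, and the tested quantity should remain all-cause.

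Nor is the baseline dose ignored altogether. SAP 9.4.9 summarises and plots opioid amount by visit, and SAP section 6 promises baseline summaries of efficacy parameters. An imbalance would be visible; the dose is absent only from the test.

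The benefit may also be small. Nothing shows how many patients enter on opioids, and when half of the prior dose persists the simulated gain is only 0.70 to 0.74. The endpoint is last of five, so it is formally tested only if the four before it succeed. These points limit the importance of the change. They do not argue for leaving a recorded, pre-treatment predictor out of the model.

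**Conclusion.** The point holds as a matter of precision only. The planned ANOVA is valid, but it forgoes a covariate that is collected before treatment and is plausibly prognostic. Over assumed correlations of 0.3 to 0.6, the variance forgone is 9% to 36%, equivalent to about 10% to 56% more patients for this endpoint. These figures rest wholly on assumption and apply to linear adjustment on the milligram scale, not to a rank-based version. If hardly any patient enters on opioids, the gain approaches zero. The documents establish that such patients may enter, not that they do. This is a free improvement.

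**What to change.** Before unblinding, amend SAP 9.4.9 to replace the one-way ANOVA with an ANCOVA. The outcome is total all-cause opioid use in oral morphine equivalents, from the first post-baseline visit through 6 weeks post-RT. Treatment is the factor and baseline morphine-equivalent dose the covariate. Align protocol 10.2.1.5, whose sum now starts at baseline, so that both documents define the same total.

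Two optional additions:

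- A rank-based ANCOVA as a sensitivity analysis for skew. It should not replace the main test, because protocol 10.2.1.5 intends a comparison of mean and median totals and ranks would drop the mean.
- A supportive table of opioid use attributed to mucositis, from the reason already coded in the eCRF. This also covers other pain that begins during RT, which baseline adjustment cannot reach.

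The cost is wording in two sections. No new data, visits or patients are needed. The timing matters, since a covariate chosen after unblinding would carry little weight.

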**Table 1: Schedule of Events by Week** 

Study week	Screen	Base 	1w 	2w	3w	4w	5w	6w	7 w	8w	9w	10w	11w	12w	13w	15- 55 w	19w	59w
Post-RT 										1w	2w	3w	4w	5w 	6w	2m-11 m 	12w	12m
Medical History	X	X	2X	2X	2X	2X	2X	2X	2X	2X	2X	X	X	X	X	X	X	X
Informed Consent	X																	
Randomization		X																
History of Pain and Opioid Use		X	2X	2X	2X	2X	2X	2X	2X	2X	2X	X	X	X	X		X	X
Assessment of Infections		X	2X	2X	2X	2X	2X	2X	2X	2X	2X	X	X	X	X			
Radiation 			5X	5X	5X	5X	5X	5X	5X									
Cisplatin 			X			X			X									
Administer Drug			2X	2X	2X	2X	2X	2X	2X	2X	2X							
WHO OM 		X	2X	2X	2X	2X	2X	2X	2X	2X	2X	X	X	X	X			
PEG Tube Use		X	2X	2X	2X	2X	2X	2X	2X	2X	2X	X	X	X	X			
VS 	X	X	2X	2X	2X	2X	2X	2X	2X	2X	2X	X	X	X	X			
Physical Exam	X	X									X 				X			
Safety Labs 	X	X 			X			X			X 		X		X			
AEs		X	2X	2X	2X	2X	2X	2X	2X	2X	2X	X	X	X	X			
Tumor Scan 	X 																X	X
Serum Pregnancy	X	X 													X			
HPV Status	X 																	
Quality of Life		X				X					X 							

<sup>1 Post-RT = time from the last radiation therapy treatment

<sup>2 Baseline information needs to be obtained prior to (0 to 96 hours before) the first dose of study drug

 $^{3}$  w = weeks

<sup>4Only to be done if WHO score is ≥2 at Week 4 Post-RT visit

<sup>5 m = months; patient contact (clinic visit, telephone, or email) required monthly through the 12-month clinic visit

<sup>6 Timing of radiation and chemotherapy at discretion of primary care physicians

<sup>7 WHO OM = oral mucositis grading with WHO Oral Mucositis Grading system

<sup>8 Vital signs to include temperature, weight, pulse, respirations, and seated blood pressure; Height will be obtained at Baseline only

<sup>9 Safety labs = hematology and clinical chemistry panels

Scan = obtain initial staging CT/PET/MRI scans (screening scan must be within 6 weeks prior to Baseline)
 Need to confirm that the initial diagnostic scans were CT, PET, or MRI and the tumor was tested for HPV status

 Repeat test required if Baseline sample >7 days from Screening 13 To be done only on the second visit in week 2 post-RT

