## 5. ANALYSIS ADJUSTMENTS DUE TO IMPACT OF COVID-19 PANDEMIC

Reference is made to the FDA Guidance for Industry, "Statistical Considerations for Clinical Trials During the COVID-19 Public Health Emergency," June 2020. While many of the patients were in the treatment portion of their participation, the COVID-19 pandemic interrupted normal clinical operations with an impact on patient retention, the number and degree of protocol deviations, the ability to obtain protocol specified measurements, the ability to ship clinical specimens, and decreased the availability of clinical research personnel to perform protocol related activities. The ultimate impact of this unprecedented disruption in the clinical trial and the resulting number of dropouts, missing data, and partial data remains unclear at this time, Currently, the protocol specifies a last-value forward method of handling missing data and all patients in the mITT population are included in the analyses even if the final 4-6 weeks of experimental therapy is not delivered. To address the impact of the pandemic on this study, we will:

- Drop patients at specific sites in which the COVID-19 activities created extensive problems with documentation, data collection and/or patient enrollment and compliance;
- Terminate the trial early; and

•	Conduct sensitivity analyses on primary, secondary and safety analyses to understand the
	potential impact of the pandemic (with an assigned "start date" to the pandemic of January 1,
	2020 based on the onset of disease potentially impacting participating European sites).

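### Total opioid use, the fifth gated secondary, is an unweighted sum of 24-hour values over an uneven visit schedule, and the missing-visit formula promised for it is not in the SAP

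*SAP*

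**What the plan says.** Opioid use is the last of five secondaries tested in fixed sequence in the mITT population: "Comparison of the total amount of opioids used" (SAP 9.3.1; also 2.2.1).

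- **What is collected.** At each visit "study personnel will record the amount of opioid medication that the patient reports having taken over the previous 24 hours" (SAP 9.4.9; protocol 10.2.1.5 agrees).
- **How the total is formed.** SAP 9.4.9 states only "Total opioid used will be summarized though the treatment period (baseline through 6 weeks post-radiation treatment"), compared by one-way ANOVA. The construction is in protocol 10.2.1.5: "total amount of opioid used for each patient summed over each visit from baseline to 6 weeks post-completion of the radiation therapy".
- **When visits occur.** Protocol 6.3.3 to 6.3.9 schedules two visits a week during RT and for two weeks afterwards, then one a week. The Week 5 post-RT visit is conditional: "Only to be done if WHO score is ≥2 at Week 4 Post-RT visit" (SAP Table 1).
- **Missed visits.** Protocol 10.2.1.5: "Patients with missing visits will have their opioid usage estimate for the missing data by using an average of their opioid use" over the available visits, "using formula detailed in the SAP". SAP 9.4.9 has no such formula. SAP Appendix 1, item 4, deals with duration of severe oral mucositis only. Item 5 says that "the protocol specifies a last-value forward method of handling missing data".

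**The concern.** A 24-hour amount is a rate in mg/day. Adding rates gives a quantity proportional to drug taken only if visits are evenly spaced. Here the spacing doubles from week 3 after RT, so a day of use in that period counts for about half as much as a day earlier on. The trial's hypothesis is a shorter duration of severe mucositis, so an opioid benefit could plausibly appear as earlier stopping, partly in that under-weighted period. A formally tested endpoint would then understate the effect it is meant to detect.

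The second problem is that the documents do not settle what a missed visit contributes. The protocol says one thing, the SAP attributes another to it, and the formula is absent. SAP section 2 and Appendix 1 expect dropouts and missing data to increase with the pandemic, so the choice could affect the result.

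**Working it through.** Neither document gives an effect size, standard deviation or missed-visit rate for opioids, so there is no plan figure to reproduce. The sample-size figure of 190 concerns the primary log-rank test and plays no part here.

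**Visit counts (protocol Table 7, SAP Table 1).** Visits = 1 baseline + 2 × (RT weeks + 2) + 3 weekly visits, or 4 if Week 5 is held. Days = 7 × (RT weeks + 6).

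| RT weeks | Visits without / with Week 5 | Days |
|---|---|---|
| 5 | 18 / 19 | 77 |
| 7 | 22 / 23 | 91 |
| 9 | 26 / 27 | 105 |

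**Weight of the late period, 7-week RT.** Post-RT weeks 3 to 6 are 28/91 = 31% of the days. They supply 3/22 = 14% or 4/23 = 17% of the values. The sampling rate is 2 days in 7 before and 1 in 7 after, which is half weight. Without Week 5 it is 3/28 against 8/28, or 0.375.

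**Effect on a treatment difference (assumed profile).** Take 80 mg/day from day 21 and 23 visits: day 0, days 2 and 5 of each of weeks 1 to 9, then days 67, 74, 81 and 88.

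- True amounts: stop at day 63, 42 × 80 = 3360 mg; stop at day 91, 70 × 80 = 5600 mg. Reduction 1 − 3360/5600 = 40%.
- Visit sums: 12 × 80 = 960 and 16 × 80 = 1280. Reduction 1 − 960/1280 = 25%.
- Trapezoid over visit dates: (4 × 40) + (38 × 80) + (6 × 40) = 3440 and (4 × 40) + (65 × 80) = 5360. Reduction 1 − 3440/5360 = 36%.

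**Equal true exposure at different times.** Assume 60 mg/day for 28 days, a true total of 1680. Placed in the twice-weekly phase, the visit sum is 480 and the trapezoid 1680. Placed in the last four weeks, the visit sum is 240 with Week 5 or 180 without it, and the trapezoid 1440 either way. The visit sum differs by a factor of 2.0 to 2.7, the trapezoid by 1680/1440 = 1.17.

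**Missing-visit rule.** Take the 80 mg/day user who leaves at day 42 of a 23-visit schedule. By then 30 weekday fractions of 2.0–2.2 Gy give 60–66 Gy, so the patient is in the mITT population. Thirteen visits are available, six of them at 80, totalling 480; ten are missed.

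| Rule | Total |
|---|---|
| Patient's average (protocol 10.2.1.5): 480/13 × 23 | 849 |
| Last value forward (SAP Appendix 1, item 5): 480 + 10 × 80 | 1280 |

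The protocol also does not say whether visits after leaving, or a Week 5 visit that was not required, count as missing.

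**The case against.** The best defence is that both arms share one schedule, so uneven weighting alone does not favour either arm. That stands: the worked example shows a benefit shrinking, not one being created. A between-arm bias would need the timing of use, Week 5 attendance or missed visits to differ by arm, and neither document shows this. SAP 9.4.9 also requires by-visit summaries and plots, so late differences would remain visible. And the endpoint is tested only if the four before it succeed.

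Three stronger readings are tempting, and the documents do not support them.

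- *Missed visits add nothing.* A reader could infer this from SAP 9.4.9 alone, which would give the day-42 leaver 480 against 1280, 62% lower. But the protocol prescribes averaging, and the SAP presents itself as elaborating the protocol. Under averaging the leaver is at 849, 34% lower.
- *The total measures visit count rather than exposure.* In a simulation with assumed onset, duration and dose, RT of 5 to 8 weeks and 0–20% of visits missed at random, the sum correlated 0.96–0.99 with true exposure and 0.10–0.15 with visit count. It tracks opioid use, with distorted weights. Nor is RT length much of an artefact: from 5 to 7 weeks, visits rise from 18 to 22 (+22%) while true days rise from 77 to 91 (+18%).
- *Visits are broadly outcome-dependent.* Only Week 5 is, at most one value in 23 (4.3%).

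It can also be argued that the last-value-forward sentence was meant for WHO grades. It may have been, but it carries no such limit.

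**Conclusion.** The point holds as a weighting and specification defect. Even with complete data, the stated visit sum gives use in post-RT weeks 3 to 6 half weight or less, and in the worked profile a 40% reduction appears as 25%. That size depends on the assumed dose profile, the assumed visit days and 7 weeks of RT. The under-weighting itself follows from the schedule alone.

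Separately, the missing-visit rule is unspecified in the SAP and inconsistent between documents: 849 against 1280 for one illustrative mITT patient. The likely consequence is a diluted effect and an analysis choice left open, not a demonstrated bias between arms. This should be corrected, but it does not threaten the primary result.

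**What to change.** In SAP 9.4.9, define each patient's total as the trapezoidal area under oral-morphine-equivalent mg/day against assessment date, from baseline to 6 weeks post-RT. Use the date-weighted sum in SAP 9.4.1 without its thresholding of scores. Missed intermediate visits are then interpolated, and a Week 5 visit that was not required is not treated as missing. The prespecified quantity, a total, is kept.

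For early leavers, state one rule consistent with protocol 10.2.1.5: average daily dose over the days covered, multiplied by the days in the patient's scheduled window. Run last value forward as a sensitivity analysis, and correct the sentence in SAP Appendix 1, item 5.

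The cost is one derived variable, one sensitivity run and a few lines of SAP text, with no new data. Two limits remain. The trapezoid depends on visit dates (36% against a true 40% above). And averaging does not fully correct leavers whose use is rising: the day-42 leaver has 1680/42 = 40 mg/day, and 40 × 91 = 3640 mg against 5600 mg had use continued, 35% lower.
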